INCLUSION AND EXCLUSION CRITERIA FOR EACH RESEARCH ACTIVITY

Research Activity #1: With approval of the NMG practice director, 15 primary care professionals will be recruited as participants, including the PHM nurse, practice administrators, physicians, and other primary care team members (e.g. nurses; health educators). Inclusion and exclusion criteria are as follows:

Table 2. Inclusion and Exclusion Criteria for Professionals Completing Interviews

Inclusions	Exclusions
Staff members employed at Northwestern Medical Group (e.g. MD, NP, PA, health educator, care manager, practice administrator) involved in the management of cardiovascular risk data collection and obesity management	NMG staff involved in protocol development

Research Activities #2, #3, and #4: With approval of the NMG practice director, eligible patients will be identified by an NMG clinical data manager performing an electronic health record data query. The query will identify patients who meet the eligibility criteria for the clinical weight management services, as detailed in Table 3 below. In this development and preliminary evaluation phase, patients targeted for the clinical services will have had 1 or more routine (non-urgent) visits to the NMG primary care practice and will have an active MyChart account with one or more log-in attempts within 12 months. Body mass index (BMI) will be determined using the last available height and weight (must be within 12 months). BMI is calculated as (weight in kg) ÷ (height in meters)². CVD risk conditions will be determined by evidence of one of the following: 1) a diagnosis of hypertension, hyperlipidemia, diabetes, or prediabetes (i.e. one or more ambulatory encounter with an ICD encounter diagnosis code or active problem specifying either type 2 diabetes, prediabetes, hypertension, or abnormal blood cholesterol); 2) an active prescription drug order for an antilipidemic class medication, long or intermediate acting insulin analog, or oral antiglycemic medication. Pregnant women will be excluded from the study, as participation involves setting a weight loss goal, which may not be medically appropriate for all pregnant women.

Patient usability testing of technology components (Research Activity #2) will occur before the pilot trial. The clinical database manager will draw names randomly from the patient eligibility list for the clinical service (Table 3), and patients will be recruited until 10 patients have completed the usability tests.

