Research Activity #3: For the pilot intervention trial, 80 overweight or obese patients with at least one cardiovascular risk factor will be recruited. With approval of the NMG practice director, eligible patients will be identified by an NMG clinical data manager performing an electronic health record data query. The query will identify patients for the clinical weight management services, as detailed in Table 3 above. Based on these criteria defining whom to target with the new clinical services, patients included in the evaluation will reflect the entire target group, having had 1 or more routine (non-urgent) visits to the NMG primary care practice, and who have an active MyChart account with one or more log-in attempts within 12 months. The clinical data manager will randomly select and generate a shorter list of 100 eligible patients from the complete eligibility list, attempting to target patients who completed a recent clinic encounter (in the preceding 1 to 3 week period). After generating this shorter list, the clinical database manager will follow a standard process for patient recruitment approved by the NMG primary care practice site by sending a MyChart staff message to each primary care provider (PCP) of those 100 patients. PCPs will be notified via Epic email regarding which of their patients are eligible and will be given the option of excluding any specific patient(s) from being recruited. PCPs will be given 5 days to respond to Epic message to exclude a patient. No response will be considered assent to recruit patient. This process will be repeated every 2 weeks until target enrollment goal (n=80) is reached. This is a standard protocol that the NMG practice has approved, as it provides sufficient advanced notification to providers, with the ability to exclude any patients as needed, while presenting minimal administrative burden to provider's existing workload.

Once eligible patients are identified, a recruitment message will be sent via Epic MyChart inviting patients to complete a MyChart survey assessing weight loss interest and goal setting as described above in **Patient-facing IT Development**. All eligible patients who receive the MyChart message and affirm their weight loss interest and goals will be included in the pragmatic evaluation sample and randomized.

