For the no-intervention comparison arm, patients will be identified from the list of approximately 1,800 remaining patients who were deemed eligible but not yet recruited before all 80 pilot intervention patients are accrued. From this list, we will select 80 patients with similar age and sex characteristics as trial participants. Patients in this no-intervention comparison group will not be contacted, will receive no intervention, and only their routinely collected clinical data will be used for the retrospective comparison evaluation (i.e. the same existing clinical data elements used to assess outcomes for the trial groups), so they will not receive contact or specific recruitment materials. Detailed information about consent and HIPAA waivers is described below in "CONSENT PROCESS" section

Research Activity #4: For the semi-structured interviews, the database manager will draw names randomly from the pragmatic trial recruitment list until 20 patients have completed the interview. After obtaining approval from the primary care provider, a research assistant (RA) will send a lead letter by email to patients and then contact each patient by phone between 8 and 12 weeks after being sent their initial MyChart message. Purposeful sampling will be used to ensure that the sample is representative of between 5 and 10 patients who did not complete the goal setting step and 10 to 15 patients who did complete that step. Phone interviews will be conducted for both patients who did not complete the goal setting step and patients who did complete the goal setting step. The RA will explain the research and assist interested participants to provide informed consent prior to completion of a one-time interview.

COMPENSATION FOR PARTICIPATION IN RESEARCH ACTIVITIES

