The goal of the evaluation is to assess the reach/uptake and effectiveness of specific new implementation strategies used to offer common health behavioral preventive services to "usual" patients under "usual" circumstances. Research procedures that introduce additional participant risks or that selectively recruit only motivated volunteers into the evaluation activities would be disruptive of busy clinical workflows and would alter

STU#: STU00207153

the findings of the evaluation in ways that are unpredictable and potentially misleading. For this reason, the pilot trial has been designed as a pragmatic, "whole population" study using data collected routinely within the clinical IT systems. The pragmatic nature of the pilot trial component (Research Activity #3) of this evaluation dictates that it could not practicably be conducted without a HIPAA waiver. This HIPAA waiver applies to the intervention, control, and no intervention groups described above under Research Activity #3. The protected health information necessary for the purposes of this evaluation are those routinely collected through clinical care and not for the sole purposes of the research. As described above, the use of this PHI involves no more than a minimal risk to the privacy of participants and a detailed plan to protect participant identifiers from improper use and disclosure is in place, as well as written assurances that the protected health information will not be reused or disclosed to any other person or entity, except as required by law, for authorized oversight of the research study, or for other research for which the use or disclosure of protected health information for which an authorization or opportunity to agree or object is not required.

For all other research activities (provider interviews; patient usability tests; patient semi-structured interviews), a HIPAA Authorization will be obtained from all participants. We are requesting the minimum necessary data available from the electronic health record that will be needed to identify potentially eligible patients who will be recruited for usability tests. Videotaped usability tests will then collect only the minimum necessary information needed to assess and improve the human-IT interaction. As we are only requesting data related to the preventive services being studied, we have made all reasonable efforts to limit the information to the minimum necessary to accomplish our intended purpose for the data set.

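### The additional comparison with the 80 no-intervention patients is open to selection bias: beyond shared eligibility they are chosen on age and sex alone

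*Protocol*

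**What the plan says.** **Trial patients.** Protocol, Recruitment Methods, Research Activity #3, describes three steps after the eligibility query.
- The data manager draws lists of 100, "attempting to target patients who completed a recent clinic encounter (in the preceding 1 to 3 week period"). This is a preference, not a criterion.
- PCPs "will be given the option of excluding any specific patient(s) from being recruited". No reply within 5 days counts as agreement.
- Patients who receive the MyChart message and "affirm their weight loss interest and goals will be included in the pragmatic evaluation sample and randomized".

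**Comparison patients.** They come from about 1,800 remaining eligible patients. The same section says: "From this list, we will select 80 patients with similar age and sex characteristics as trial participants". They are not contacted, and only routinely collected clinical data are used. The protocol calls the purpose additional comparisons.

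**Baseline.** Under Inclusion and Exclusion Criteria, eligibility BMI "will be determined using the last available height and weight (must be within 12 months"). The SAP (Data Sources & Collection) takes the last health-record weight before randomization as baseline, and the weight nearest day 180 as follow-up.

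**Analysis.** The SAP's Statistical Analysis section compares the randomized arms. It names ANCOVA and logistic models but no covariates. The SAP text available does not mention the no-intervention group.

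**The concern.** Both randomized arms receive intervention components 1 to 4, so C3PO versus BRS isolates component 5. The no-intervention group gives the only contrast with patients who receive none of the package, and a reader may take it as the effect of the whole package.

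Under the stated rule, the two sides of that contrast differ in more than the intervention. Everyone in the trial said that they wanted to lose weight, whereas the comparison patients were never asked. Trial patients probably have fresher baseline weights. Only trial patients are described as having passed PCP review.

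The protocol sees a related hazard in its case for the HIPAA waiver. It says that procedures that "selectively recruit only motivated volunteers into the evaluation activities would be disruptive of busy clinical workflows and would alter" "the findings of the evaluation in ways that are unpredictable and potentially misleading". That passage concerns research procedures in the pilot, not the comparison group. The same reasoning applies with more force where one side is selected on interest and the other is not.

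At stake is how the contrast is interpreted, and whether it is later used as an effect size when the larger trial is designed.

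**Working it through.** **1. The plan's own figure.** Total accrual is 15 + 10 + 80 + 20 + 80 = 205, which agrees with the protocol. No power, alpha or effect size is given for this comparison, so there is nothing else to reproduce.

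**2. The two groups side by side.**

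| Step | Trial patients | Comparison patients |
|---|---|---|
| Table 3 eligibility | Yes | Yes |
| Recent encounter | Sought by preference | Not described |
| PCP exclusion | Yes | Not described |
| Interest and goals affirmed | Required | Never asked |
| Similar age and sex | Reference group | Yes |
| Anchor date for baseline | Randomization | None given |

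**3. Interest (all rates assumed).** Let q be the share of eligible patients who would affirm interest. Let p1 and p0 be the untreated 5%-loss rates in interested and other patients. If comparison patients are an unselected mix, the gap with no intervention effect is p1 - [q·p1 + (1 - q)·p0] = (1 - q)(p1 - p0). With p0 = 10%, in percentage points:

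| q | p1 = 7% | p1 = 15% | p1 = 20% |
|---|---|---|---|
| 20% | -2.4 | +4.0 | +8.0 |
| 40% | -1.8 | +3.0 | +6.0 |
| 60% | -1.2 | +2.0 | +4.0 |

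For scale, the 95% half-width at a 15% rate is 1.96·√[0.15·0.85·(1/80 + 1/80)] = 11.1 points for 80 versus 80. For one arm of 40 versus 80 it is 13.6 points. A bias of this size would not be visible in the data.

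**4. Age of baseline (assumed no-drift random walk).** Let percent weight change over t months have SD s·√(t/6), with s = 3, 4 or 5. Then P(loss ≥ 5%) = Φ(-5 / [s·√(t/6)]). Gaps are taken before rounding, and negative values favour the comparison group.
- Trial interval 6 months: 4.8%, 10.6%, 15.9%.
- Comparison baseline 3 months older (9 months): 8.7%, 15.4%, 20.7%. Gaps: -3.9, -4.8, -4.8 points.
- Comparison baseline 6 months older (12 months): 11.9%, 18.8%, 24.0%. Gaps: -7.2, -8.3, -8.1 points.
- Small case: four evenly spaced clinic weights a year give a mean baseline age of 1.5 months, against about 0.5 month for trial patients. The intervals are 7.5 and 6.5 months, and the gaps are -1.3, -1.7 and -1.7 points.

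**5. Missing weights.** The SAP counts a missing weight as failure. At a 15% rate, a difference in weight capture of 5 to 20 points shifts the contrast by 0.15 × 5 = 0.75 to 0.15 × 20 = 3.0 points towards the better-captured group.

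**6. The source list.** The protocol gives 5,967 eligible patients and about 1,800 remaining, a difference of 4,167. At 100 per list every two weeks, that would take about 42 lists, or 83 weeks. The SAP's randomization dates (12/16/2019 to 1/6/2020) span 21 days. An unstated filter may have applied. If it involved visit recency, step 4 shrinks further.

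**The case against.** The strongest reply is that little depends on this comparison. The study is a pilot, the group is for additional comparisons, no test or decision rule is attached to it, and no passage says that it will supply planning effect sizes. Part of the SAP was not available, so its silence cannot be firmly held against the plan. This stands, and it is why the point is minor.

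A second reply is that the figures are all assumed and point both ways. That also stands. They show what the stated rule allows, not what happened. The share affirming interest cannot be recovered by dividing 80 by the lists that fit the 21-day window, because those are randomization dates, not list dates.

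Third, matching cannot restore comparability on interest, because uncontacted patients were never asked. This limits the fix. It does not help the current rule.

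A reader might infer more than the documents support:
- **That the randomized result is biased.** Interest, visit targeting and PCP exclusion all act before randomization, so they apply equally to both arms.
- **That the contrast flatters the intervention.** Interest and older baselines can act in opposite directions.
- **That comparison patients cannot meet the primary outcome because no goal was asked of them.** The SAP applies that outcome to the randomized arms. In the protocol's data list, MyChart lifestyle goals are not marked as inapplicable to this group.

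**Conclusion.** The concern holds for the non-randomized comparison only. Beyond shared eligibility, the stated rule equates the groups on age and sex. It leaves differences in weight-loss interest, PCP exclusion and probably recency of the baseline weight. No index date for the comparison patients is given in the text available.

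Neither the size nor the net direction of the bias can be derived from the documents. The illustrations run from -2.4 to +8.0 points for interest. For baseline age they run from about -1.3 to -8.3 points, and only 1 to 2 points if clinic weights are frequent. Both rest on assumed rates; the second also assumes a no-drift random walk and recent trial baselines, which targeting by preference does not guarantee.

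This is a minor point and a cheap improvement.

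**What to change.** 1. State how the list of about 1,800 was formed from the 5,967 eligible patients, because this determines which recency match is feasible. Then give each comparison patient the randomization date of a matched trial patient as index date. Match on baseline BMI, cardiovascular risk conditions and recency of the last health-record weight, as well as age and sex. Where the pool is too small, adjust instead.
2. For this comparison only, use weight change and loss of at least 5% from health-record weights, without the goal element or eScale values. Apply the same windows and missing-data rule in all three groups, and report weight capture by group.
3. Report the contrast as descriptive. State that interest and PCP exclusion remain unmatched, and do not use it as an unbiased effect size for the next trial.

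The cost is one revised record query and one table, using fields already in the Research Activity #3 data list. The downsides are a smaller matching pool, eScale-only outcomes left unused in this comparison, and residual confounding by interest. If selection is already complete, the adjustment, common outcome and labelling can still be applied at reporting.

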## Analysis Plan

**Data Sources & Collection:** The primary outcome of interest was the percent of eligible patients who commit to a weight goal and reach 5% or greater weight loss at 6 months. Key secondary outcomes include the percent of eligible patients who set a weight goal (regardless of weight loss), and mean changes in pragmatically collected cardiometabolic risk factors. As a feasibility study, we also estimated costs per person per year for intervention delivery.

We assessed the feasible capture of body weight measures from two pragmatic data sources: electronic health records and cellular-enabled, wireless body weight scales (eScales), which were provided to all participants at the time of randomization. We extracted the date and value of all body weight recordings in the electronic health record of each eligible patient participant during the 12 months before his/her study randomization date (each occurred between 12/16/2019 and 1/6/2020). We also extracted the date and value for all body weight measures available from either the electronic health record or from eScale transmissions during the 15-month period after each individual's study randomization. The last electronic health record weight measure prior to the randomization date served as the baseline body weight for constructing the primary weight change outcome variable. The electronic health record weight measure closest to the date of randomization plus 180 days (6 months) was selected for the follow up body weight measure for the primary outcome analysis. For patients who did not have a follow up weight value in the electronic health record between 6 months +/- 3 months, we searched the electronic health record for a weight value between 12 months +/- 3 months. For participants missing 6-month weight values, we imputed their 6-month value as equal to one half the distance between the baseline and 12 month value. For participants missing both a 6- and 12-month weight value in the electronic health record, we used the eScale weight value closest to 6 months +/- 3 months. Finally, if individuals were missing all of these weight values, we assumed conservatively for the primary outcome analysis that the participant failed to reach the 5% weight loss threshold. All blood pressure, A1c, and cholesterol test results were extracted similarly from the electronic health record. As this was a small pilot trial, when analyzing mean change at different time points, we analyzed only those patients with available outcome measures and did not use advanced imputation approaches for replacing missing values.

**Statistical Analysis:** We examined univariate and bivariate descriptive statistics and conducted chi-square or Fisher exact tests to compare all patients randomized to intervention and control arms on the proportion that reached the dichotomous primary outcome of clinically meaningful weight loss at 6 months. We conducted t-tests to compare all patients with available outcome measures in each study arm with respect to all pre-specified, continuous outcomes (e.g., mean changes in body weight, systolic blood pressure, hemoglobin A1c, total cholesterol, and non-HDL cholesterol). Multivariate models (ANCOVA and multivariate logistic regression) were used to estimate adjusted means (continuous variables) or proportions (categorical variables) for each pre-specified outcome. We explored stratified analyses by age and by sex to understand if preliminary outcome differences appeared to vary with these biologic variables.

Input from health system leaders and study team members were used to identify the principal "ingredients" of study interventions. Inputs included personnel, supplies, contract services, and facility and administrative costs, all from the perspective of the health system. Administrative data on the number and type of contacts made between nurses and study participants, as well as interviews with staff to identify time spent in other activities was used to estimate %FTE spent with patients in each study arm over 6 and 12 months. Costs of eScales and community intervention program fees were estimated from the invoice amounts to estimate cost per person and overall. One-time development or startup costs for health IT was estimated from contract amounts and invoiced payments for work performed. Operational or maintenance costs for IT support was estimated from interviews of IT staff members, who were asked to estimate hours per week spent supporting the intervention components. Research-only costs were excluded from intervention cost estimations. Since many health payers currently reimburse for lifestyle interventions costing between \$400 and \$800 per person annually, preliminary estimates for intervention costs equal or less than this were considered supportive of health system sustainability and were used as a threshold for proceeding to a larger future trial that will include a more intensive net cost and cost-effectiveness analysis.

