The novel combination of existing lifestyle intervention components resulting from phase 1 of the research will subsequently be evaluated using a pragmatic randomized intervention design. The goal of this research is to evaluate the new cluster of interventions, which we call Coordinating Pragmatic Primary care Population management for Obesity (C3PO), among a sample of patients who are representative of all patients who might be offered the intervention in routine practice. Thus, instead of recruiting highly selected research volunteers for the pilot trial, we will use a pragmatic randomization design that will use a “behind the scenes” randomization approach to assign 80 eligible patients to receive Basic Resources and Services for healthy lifestyle support (n=40) or the C3PO pilot intervention (n=40). We will not collect data for research purposes only in this trial. Rather, we will use routinely collected clinical data (i.e. available from the electronic health record) for each patient. Following completion of the 4-month pilot trial phase, we will then recruit and consent 20 patients who were eligible for the intervention to complete semi-structured interviews to assess patient experiences, perceptions, and barriers faced during the intervention period. This final step will help to inform any additional relevant intervention refinements prior to conducting a larger and more definitive future trial of the intervention’s effectiveness.

Figure 1. Development & Pre-Testing of a Novel Intervention for Coordinating Pragmatic Primary care Population management for Obesity (C3PO)

THE INTERVENTION DEVELOPMENT PHASE HAS 4 GENERAL OBJECTIVES:

- 1) **ASSESS HEALTHCARE PROVIDER PERCEPTIONS REGARDING C3PO INTERVENTION NEEDS, PRIORITIES, AND PREFERENCES**
- 2) **ASSESS EXISTING RESOURCES & WORKFLOWS**
- 3) **INTEGRATE EXISTING WORKFORCE, WORKFLOW, AND IT COMPONENTS NEEDED FOR POPULATION HEALTH MANAGEMENT TO BE EFFICIENT AND EFFECTIVE**
- 4) **PRETEST IT COMPONENTS USING LIMITED PATIENT USABILITY TESTING**

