- 2) **Self-monitoring of Body Weight:** Prior research suggests that process accountability (e.g. accountability over self-weighing) increases completion of a target behavior even more than outcome accountability alone (e.g. accountability over achieving a weight loss goal).¹³ Self-weighing is a form of behavioral self-monitoring that past research has found to be strongly predictive of weight loss success.¹² C3PO will provide each patient with a BodyTrace electronic scale (eScale), which transmits weight data wirelessly to a secure, private repository using digital mobile telecommunications technology (i.e. the same cellular networks as a smartphone). The manufacturer reports accuracy within +/-0.1 kg to a weight limit of about 150 kg (330 lbs.).⁸¹ This approach, used in prior research by our group,⁸² also enables the seamless integration of self-weighing information back into the EpicCare EHRS (i.e. back to the registry as well as to the PHM nurse). This integration will allow dynamic individualized feedback from the nurse back to each patient in a way that further strengthens supportive accountability and progress toward weight goals. More details are provided below.
- 3) **Supportive Accountability for Achieving Self-management Goals and Objectives:** Nurse-patient interactions, largely facilitated by the patient portal, will be designed to strengthen each patient's commitment toward their goal, as well as a greater sense of "**supportive accountability.**" Accountability toward a behavior exists when an individual has an expectation that he/she may be called upon to justify his/her actions or inactions to another person.¹³ Accountability requires real or perceived social interactions with another human (i.e. a coach) who the patient views as trustworthy and possessing suitable expertise. This relationship may be established in person, by telephone, or via an electronic channel. C3PO will utilize secure patient-facing EHRS technologies to deliver recommendations of the patient's own primary care provider via the practice team's PHM nurse. For patients who request additional information or assistance in goal setting or decision making, the PHM nurse will offer a telephone or face-to-face encounter as an alternative. The planned approaches for supporting goal setting, self-monitoring, and intensive intervention linkages are described further below.

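### For the primary outcome, half of a later clinic weight change, whatever the visit date, is used ahead of a measured 6-month eScale weight (minor)

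*SAP*

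**What the plan says.** The SAP (Analysis Plan, Data Sources & Collection) defines the primary outcome as "the percent of eligible patients who commit to a weight goal and reach 5% or greater weight loss at 6 months". Baseline is the last EHR weight before randomization. The follow-up weight is then found in this order:

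1. The EHR weight closest to day 180, within 6 ± 3 months.
2. If there is none, an EHR weight at 12 ± 3 months, from which "we imputed their 6-month value as equal to one half the distance between the baseline and 12 month value".
3. For patients "missing both a 6- and 12-month weight value in the electronic health record, we used the eScale weight value" closest to 6 months, within ± 3 months.
4. If all of these are missing, the patient is counted as not having reached 5%.

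The SAP says that eScales went to all participants at randomization. It also says: "We also extracted the date and value for all body weight measures available from either the electronic health record or from eScale transmissions", over the 15 months after randomization. The SAP (Statistical Analysis) says that the team "conducted chi-square or Fisher exact tests to compare all patients randomized to intervention and control arms" on this binary outcome. The Protocol (Phase 2: Intervention Evaluation) says "We will not collect data for research purposes only in this trial", so no study visit secures a clinic weight at 6 months. The SAP gives no reason for placing step 2 above step 3 and describes no sensitivity analysis of the order or of the one half.

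**The concern.** Two features of step 2 stand out.

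- **Order.** A constructed value outranks a weight measured in the 6-month window. A patient with a home-scale loss of 8% at month 6 and no clinic weight in either window is a success at step 3. If a month-10 clinic visit confirms the 8%, the same patient moves to step 2, is scored 4%, and fails. More confirming data reverses the classification.
- **Date.** The fraction is one half whether the later visit falls at month 9 or month 15. For straight-line change, one half is right only at day 360.

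For patients on this path the endpoint is therefore a 10% loss at months 9 to 15, not a 5% loss at month 6. The trial is meant to give preliminary effect sizes for a larger trial, so a distorted response rate could carry forward.

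**Working it through.** **From the documents.** Threshold 5%; fixed fraction 0.5; later window 12 ± 3 months (about days 271 to 450); 40 patients per arm. The documents give no figure for the number of patients on step 2, for weight courses, or for eScale availability, so there is no figure of the plan's own to reproduce.

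**Later loss needed for success on step 2.**
- Fixed half: 5 / 0.5 = 10%, at any date.
- Straight line to day 180: 5 × d / 180, which is 7.5% at day 271, 10% at day 360 and 12.5% at day 450.

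**Single patients under the fixed half.**
- Sustained loss of 5% to 9.9%: scored 2.5% to just under 5%, failure.
- 3% at month 6 and 10% at month 12: scored 5%, success.

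**Illustration, step-2 patients only.** Assumed, not in the documents: 6-month loss normal with mean 3% and SD 5%; later loss has the same mean and SD (loss maintained on average); correlation 0.8.
- True response: P(N(3, 5) ≥ 5) = 34.5%.
- Scored response: P(N(3, 5) ≥ 10) = 8.1%.
- Status wrong, by simulation with 2 million draws: about 27% (23% to 30% over SD 3 to 7 and correlation 0.6 to 0.95). Nearly all of these are true responders scored as failures.

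**Effect of each alternative.** Later visits are uniform over days 271 to 450. An eScale weight is available for 50% at random, with measurement error SD 1%. The cells give the share misclassified.

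| Assumed later course | Fixed half | 180 / days | eScale first |
|---|---|---|---|
| Maintained, SD 5% | 27.2% | 26.9% | 16.5% |
| Mean doubled, SD 5% | 20.1% | 21.0% | 13.0% |
| Mean doubled, SD 10% | 18.9% | 19.3% | 12.3% |

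The source order matters more than the date. Date scaling rescues a sustained 8% loss only if 8 × 180 / d ≥ 5, that is, for visits up to day 288. The date does matter if weight really follows a straight line. The fixed half then requires a 6-month loss of 1800 / d, and gives 23.3% response at day 271, 34.5% at day 360 and 42.1% at day 450, against a true 34.5%.

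**Size in an arm of 40.** One reclassified patient is 1/40 = 2.5 points. With loss maintained and an assumed 4, 8 or 12 patients on step 2, the net responders lost are n × (0.3446 − 0.0808) = 1.1, 2.1 or 3.2, which is 2.6, 5.3 or 7.9 points.

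**The case against.** **Clinic weights first keeps one source.** Baseline is a clinic weight, so clinic follow-up avoids an offset between clinic and home scales. That supports a measured clinic weight at step 1. It does not support a constructed one at step 2, and step 3 already accepts an eScale weight against the clinic baseline for this same endpoint.

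**eScale availability may depend on arm or outcome.** This stands. Only the C3PO arm receives follow-up tied to self-weighing (Protocol, Patient-facing IT Development and Research Activity #3), and the Protocol describes self-weighing as a behaviour that "past research has found to be strongly predictive of weight loss success". With identical outcomes, loss maintained and assumed availability of 70% against 40%, ranking the eScale first creates a false difference of 0.3 × (34.7% − 8.1%) = 8.0 points among step-2 patients. The 34.7% is the response measured with the 1% scale error. An in-window eScale weight may also be taken well before or after day 180, as may a step-1 clinic weight.

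**Redefining the primary after extraction is worse than the flaw.** This also stands. The SAP is written in the past tense, and date scaling gains almost nothing on average. If weight is flat after month 6, date scaling also makes the result depend on visit timing: visits at day 300 in one arm and day 400 in the other give 14.3% against 5.2%, a false 9.1 points where the fixed half gives none.

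**A stronger reading.** A reader might infer that the rule biases the comparison of arms in a known direction. The documents do not support that. The rule is the same in both arms. With assumed 6-month means of 5% and 3% (SD 5%), the true difference is 15.5 points. The rule gives 7.8 if loss is maintained. If mean loss doubles by the later visit, it gives 28.8 (later SD 5%) or 15.5 (later SD 10%). The later weight course is not given, so neither dilution nor inflation can be claimed. Nor can it be inferred that the trial's result is wrong, because step 2 may hold few patients or none.

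**Conclusion.** The point holds as a minor one. The stated order puts a constructed value ahead of a measured 6-month weight, and the constructed value takes no account of visit date. On that path a sustained 5% to 9.9% loss fails even where the home scale shows success, and a late 10% loss passes even if the 6-month loss was only 3%.

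The text and the 10% threshold are certain. The 27% misclassification rests on the assumed mean, SD, correlation and maintained loss, and applies only to patients on step 2, whose number is unknown. No false difference between arms is expected if weight courses and visit dates match by arm. The source order is the main issue; the date is secondary.

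**What to change.** Keep the SAP's rule as the primary analysis. Add two sensitivity analyses, both labelled post hoc because the data had already been extracted:

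1. The primary outcome with a measured eScale weight at 6 ± 3 months ranked ahead of any imputation, against the same EHR baseline.
2. The primary outcome with the fixed half replaced by 180 / (days from randomization to the later EHR weight).

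Report per arm the number scored at each of the four steps, the number on step 2 who also have an in-window eScale weight, and the days of the clinic and eScale weights used. If the analyses disagree, qualify the primary result.

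The cost is a short paragraph, a few lines of code and one table, since the dates and values are already extracted. If step 2 is empty, the table shows that the point has no effect. The main downside is that the eScale-first analysis can itself bias the difference if availability varies by arm or with outcome. For that reason it belongs beside the primary with its counts, not in its place.
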